Any supplemental information that may be added to this document is also confidential and proprietary to Novartis and CCTG and must be kept in confidence in the same manner as the contents of this protocol. Publication will proceed per policy and as per protocol. Novartis require a review period of fifteen (15) working days for presentation materials and abstracts and forty-five (45) working days for manuscripts.

Please note: Novartis has not provided a contractual indemnification to investigators or study sites for any claims arising out of or in connection with the administration or use of the drugs being studied through the study ("study drugs") during the course of this study.

Qualified Investigator
(printed name and signature)

Date

Institutional Representative
(printed name and signature)

Date

Protocol Number: CCTG IND.216

CENTRE: _____

AMEND #1: 2015-OCT-22; AMEND #2: 2016-JAN-04; AMEND #3: 2016-AUG-24

TREATMENT SCHEMA

A phase II study of buparlisib in patients with relapsed and refractory chronic lymphocytic leukemia.

Eligibility Criteria

- Previously documented CLL as defined by the 2008 International Workshop on Chronic Lymphocytic Leukemia (IWCLL) Guidelines that is recurrent or relapsed after previous therapy and that requires treatment (see Appendix VI);
- Measurable disease with at least one of lymphocyte count $\geq 10 \times 10^9/L$ *OR* at least one pathologically enlarged lymph node ($\geq 2 \times 2$ cm) by CT scan;
- ECOG performance status of 0, 1 or 2;
- At least one prior systemic treatment regimen (single agent or combination therapy, may include autologous or allogeneic stem cell transplantation) and have recovered from all reversible toxicity related to prior systemic therapy and have adequate washout period (See Section 5.1.6);
- Age ≥ 18 years;
- Life expectancy of at least 12 weeks;
- Neutrophils $\geq 1.0 \times 10^9/L$;
- Platelets $\geq 50 \times 10^9/L$ and more than 5 days since last transfusion;
- Creatinine clearance ≥ 50 mL/min;
- Bilirubin $\leq 1.5 \times$ upper normal limit (UNL) (direct if known Gilbert's);
- AST and ALT $\leq 1.5 \times$ UNL ($\leq 3 \times$ UNL if hepatic involvement with CLL);
- Potassium and calcium (within normal limits for laboratory (supplementation permitted));
- Fasting glucose < 7.8 mm/L (AND HbA1c $\leq 8\%$ if diabetic).

Ineligibility Criteria

- Prior treatment with buparlisib (BKM120);
- Progression to high grade lymphoma or myelodysplasia;
- History of other malignancies, except those which have been curatively treated and require no ongoing therapy;
- Known hypersensitivity to study drug or its components;
- Serious illness or medical condition;
- Uncontrolled or significant cardiovascular disease including left ventricular ejection fraction $< 50\%$;
- Mood disorders (see Section 5.2.6);
- Impairment of gastrointestinal function or GI disease that may significantly alter the absorption of buparlisib;
- Patients unable to swallow capsules;
- Patients on strong CYP3A inhibitors/inducers or therapeutic doses of warfarin-like anticoagulants;
- Patients on drugs with a known risk to induce Torsades de Pointes (see Appendix VIII)
- Patients receiving high dose steroid therapy or another immunosuppressive agent;
- Patients with known HIV positivity;
- Patients with known CLL involvement of the central nervous system.

AMEND #1: 2015-OCT-22

Pre-Treatment Evaluations

- History, physical exam, vital signs, ECOG performance status, toxicity/baseline symptoms, 12-lead ECG (within 7 days prior to registration);
- Hematology, biochemistry and coagulation (within 7 days prior to registration);
- Mood Questionnaires (within 7 days prior to registration);
- MUGA/LVEF (only if clinically indicated) (within 28 days prior to registration);
- Pregnancy test (within 7 days prior to registration) (if applicable);
- Direct anti-globulin test (DAGT) (within 7 days prior to registration);
- CT scan of neck, chest, abdomen and pelvis (within 21 days prior to registration);
- Bone marrow aspirate and biopsy for routine local pathology to assess CLL (within 28 days prior to registration);
- Hepatitis B surface antigen (HBsAg) (within 28 days prior to registration);
- Hepatitis C serology (within 28 days prior to registration);
- Fluorescence in situ hybridization (FISH) for 17p and 11q deletion (within 28 days prior to registration);
- Immunoglobulin variable region (IgV_H) mutation status (any time prior to registration);
- Peripheral blood for correlatives (within 28 days prior to registration).

Treatment

- Buparlisib will be given orally daily starting day 1 cycle 1. A cycle is defined as 28 days of treatment.

On Treatment Evaluations

- Physical exam, ECOG, vital signs (Day 1 each cycle);
- Hematology and Biochemistry (Days 1 and 14 cycle 1 and 2, then Day 1 each cycle thereafter; more frequently if clinically indicated);
- CT scan of neck, chest, abdomen and pelvis. (To be repeated 8, 16, and 24 weeks from registration and thereafter every 12 weeks. Patients who have no evidence of disease on CT at baseline can omit follow up scans unless palpable disease arises or there is clinical suspicion of disease progression.);
- Bone marrow aspirate and biopsy (at time other criteria for CR first met and 8 weeks later to confirm sustained CR; or if cytopenia of uncertain cause) (see Section 9);
- Assessment for minimal residual disease (MRD) (Optional – if CR criteria otherwise met) (see Section 9);
- Mood Questionnaires (Day 1 and 14 in cycles 1 and 2, then Day 1 each cycle and End of Treatment visit);
- Correlative blood work (At time of disease progression-if applicable) (See Section 17 and Laboratory Manual);
- Adverse events -patients to be evaluated continuously for adverse events.

Correlative Blood Work

- See Section 17 and Laboratory Manual.

Duration of Treatment

Patients may stop protocol treatment in the following instances:

- Intercurrent illness which would, in the judgment of the investigator, affect assessments of clinical status to a significant degree, and require discontinuation of protocol therapy.
- Unacceptable toxicity as defined in Section 8.0;
- Tumour progression or disease recurrence as defined in Section 10.0;
- Request by the patient;
- Completion of therapy as outlined in Section 8.0. Efforts should be made to maintain the investigations schedule and continue follow-up, even if patients discontinue protocol treatment prematurely and/or no longer attend the participating institution.

1.0 OBJECTIVES

1.1 Primary Objective

To determine the overall response rate (complete + partial response) to oral buparlisib in patients with relapsed and refractory chronic lymphocytic leukemia.

1.2 Secondary Objectives

- 1.2.1 To evaluate the safety and tolerability of buparlisib administered at 100 mg per day on a 28 day cycle, in patients with previously treated chronic lymphocytic leukemia.
- 1.2.2 To evaluate additional measures of efficacy including:
 - duration of response rate
 - progression free survival
- 1.2.3 To explore potential molecular factors which may be prognostic or predictive of response or of relapse including:
 - correlation between clinical response to buparlisib and MTT assay (cell viability assay) in B-CLL exposed ex-vivo to buparlisib
 - correlation between response to buparlisib and western blot and flow cytometry analysis of key proteins involved in the PI3K pathway
 - identification of mechanisms of resistance among patients who relapse after therapy with buparlisib
- 1.2.4 To prospectively validate a survival prediction scale.

2.0 BACKGROUND INFORMATION AND RATIONALE

Chronic lymphocytic leukemia (CLL) is characterized by the accumulation of malignant B lymphocytes expressing the surface antigens CD19, CD20, CD23 and CD5 [Klein 2001]. These B-CLL cells display altered apoptosis that is caused by both primary tumour features and co-dependent stromal elements [Burger 2000]. Current treatments for this disease include alkylating agents (chlorambucil, cyclophosphamide, bendamustine), purine analogs such as fludarabine, and immunotherapeutic agents (rituximab, alemtuzumab), either given as single agents or in combination. The current gold standard for CLL treatment is fludarabine, cyclophosphamide and rituximab (FCR). However, none of these standard treatments result in cure, supporting the need for investigation of new therapeutic targets and drug development in CLL as well as markers that can predict clinical response to therapy [Gribben 2011].

[figure not shown]
The phosphatidylinositol 3-kinase (PI3K) cascade is a critical component of survival signaling including PI3K-activated Akt (phosphorylated Akt) which inhibits cell death pathways by inactivating pro-apoptotic proteins such as Bad, procaspase-9 and members of the Forkhead transcription factor family. Overexpression of PI3K appears to play a critical role in B-CLL cell survival. Recently, the PI3K δ inhibitor idelalisib showed preclinical activity in CLL lymphocytes and is now in clinical trials in combination with chemotherapeutic and immunotherapeutic agents in patients with relapsed B-cell malignancy including CLL [Herman 2010, Lannutti 2011, Furman 2014]. The pan class I PI3K inhibitor buparlisib (BKM120, Novartis Pharma AG, Basel, Switzerland) is currently under investigation in phase I, II and III clinical trials in patients with advanced solid tumours [Bendell 2012], clinicaltrials.gov.

In view of the critical role of PI3K in CLL homeostasis [Liu 2009], *in vitro* cytotoxic effect of buparlisib was assessed in 3 B-CLL cell lines and in primary B-lymphocytes isolated from 65 B-CLL patient samples utilizing the MTT assay. The IC₅₀ (drug concentration resulting in 50% cell death) obtained in the B-CLL cell lines JVM2, EHEB and MEC2 were 0.9 \pm 0.1, 0.7 \pm 0.1 and 0.7 \pm 0.1 μ M respectively. Buparlisib was cytotoxic (IC₅₀ below the maximum concentration (20 μ M) of buparlisib used in the MTT assay) in 78% of the primary B-CLL lymphocyte samples tested. It is known that patients whose CLL bears a 17p (del17) or 11q (del11) deletion have a poorer response to standard therapy and a shortened overall survival [Grever 2007]. Buparlisib was demonstrated to be cytotoxic in all patient samples harboring these deletions [Amrein 2013].

In the phase I clinical study, the maximum plasma concentration (C_{max}) of buparlisib obtained after administration of the maximum tolerated dose of the drug was 5 μ M [Grever 2007]. Interestingly, 60% of the B-CLL samples tested by Amrein [Amrein 2013] have an IC₅₀ below this C_{max}. Furthermore, 5 out of the 6 patient samples with del11 or del17 have a clinically achievable IC₅₀. These results indicate that buparlisib may be useful as a single agent in CLL. MTT assay demonstrated buparlisib to be 3.6 times more toxic than idelalisib in malignant B-CLL lymphocytes *in vitro* in 20 patient samples. Furthermore buparlisib was cytotoxic (IC₅₀ $<$ 20 μ M) in 80% of these 20 samples tested while idelalisib was only cytotoxic (IC₅₀ $<$ 50 μ M) in 45% of these samples. CLL has a widely variable response to therapy. Positive correlations were observed between buparlisib cytotoxicity and the basal expression of Akt ($r = 0.592$, $p = 2.468E-06$, $n = 54$), rictor ($r = 0.418$; $p = 1.65E-03$; $n = 54$), raptor ($r = 0.463$; $p = 4.5E-03$; $n = 54$), p70S6K ($r = 0.584$, $p = 3.561E-06$, $n = 54$) and 4E-BP1 ($r = 0.371$, $p = 5.75E-03$, $n = 54$) but not with PTEN, mTOR, IgVH or CD38 expression. Only patients very sensitive to buparlisib (IC₅₀ \leq 3 μ M) expressed low basal levels (below the cut off) of mTOR, raptor and p70S6K simultaneously. Thus, simultaneous expression of low basal levels of these three proteins may be useful to predict response to buparlisib.

In vitro studies have identified that stromal cells promote cell survival and drug resistance of B-CLL lymphocytes by cell-cell interaction and secretion of chemokines [Hayden 2012]. Buparlisib induced apoptosis in primary B-CLL lymphocytes both in the presence, and in the absence of BMS2 stromal cell support, indicating that malignant lymphocytes are not protected against the cytotoxic effect of buparlisib by the stromal microenvironment [Amrein 2013]. There is increasing evidence that the major cause of resistance to therapy in CLL patients is a consequence of a small number of leukemic cells that remain after treatment. This phenomenon, called minimal residual disease (MRD), is in part a consequence of protection conferred by the stromal microenvironment to the malignant lymphocytes; eradication of MRD by alemtuzumab and other agents improved overall and treatment-free survival in CLL patients [Hayden 2012, Moreton 2005].

Although many patients are asymptomatic at diagnosis, CLL is a progressive disease and most patients eventually require treatment. Standard chemo-immunotherapy regimens are not curative and most patients require retreatment for their disease. Preclinical results demonstrate that the class I PI3K inhibitor buparlisib may be useful as a single agent in CLL patients independently of their IgVh mutational status, CD38 expression or genomic deletions (del11 and del17). Furthermore, combination of different biomarkers (expression of mTOR, raptor and p70S6K) may predict the response to buparlisib treatment. Also, buparlisib abolishes the protection against apoptosis and drug resistance conferred by the microenvironment to the primary B-CLL lymphocytes *in vitro*. For these reasons, this clinical trial will test buparlisib in patients with relapsed and refractory CLL. The efficacy of buparlisib will be determined and predictors of response to therapy will be validated. Ultimately, the identification of predictive biomarkers can help personalize the use of PI3K inhibitors in patients with CLL.

CONFIDENTIAL

AMEND #3: 2016-AUG-24

A large black rectangular redaction box covers the upper two-thirds of the page. A small black square is located in the top-left corner of this redacted area. A thin black horizontal line is positioned at the very bottom of the page, just above the footer area.

4.0 TRIAL DESIGN

This is an open-label, single-arm phase II study of buparlisib, 100 mg orally daily for patients with relapsed or refractory chronic lymphocytic leukemia. This trial is being conducted by the Canadian Cancer Trials Group, with support in the form of partial funding and study drug provision from Novartis.

5.0 STUDY POPULATION

This study is designed to include women and minorities as appropriate, but is not designed to measure differences in intervention effects.

5.1 Eligibility Criteria

There will be NO EXCEPTIONS to eligibility requirements at the time of registration. Questions about eligibility criteria should be addressed prior to registration.

The eligibility criteria for this study have been carefully considered. Eligibility criteria are standards used to ensure that patients who enter this study are medically appropriate candidates for this therapy. For the safety of the patients, as well as to ensure that the results of this study can be useful for making treatment decisions regarding other patients with similar diseases, it is important that no exceptions be made to these criteria for admission to the study.

Patients must fulfill all of the following criteria to be eligible for admission to the study:

5.1.1 Previously documented CLL as defined by the 2008 International Workshop on Chronic Lymphocytic Leukemia (IWCLL) guidelines [Hallek 2008] that is recurrent or relapsed after previous therapy and that requires treatment (see Appendix VI).

5.1.2 Age \geq 18 years.

5.1.3 ECOG Performance Status score of 0, 1 or 2 (See Appendix II).

5.1.4 Patients must have a life expectancy of at least 12 weeks. Those who have previously completed curative treatment of a malignancy other than CLL will be eligible.

5.1.5 Patients must have at least ONE of:

Lymphocyte count $\geq 10 \times 10^9/L$

OR

At least one pathologically enlarged lymph node ($\geq 2 \times 2$ cm) by CT scan

5.1.6 Previous Therapy

Patients must have received at least 1 prior systemic treatment regimen (single agent or combination therapy). There is no upper limit on number of prior regimens. Patients who have received prior autologous or allogeneic stem cell transplantation are eligible.

Patients must have recovered (to \leq grade 2) from all reversible toxicity related to prior systemic therapy, and have adequate washout from prior chemotherapy and investigational agents defined as the longest of:

- two weeks
- standard cycle length of prior regimen (e.g. 28 days for FCR)
- 5 half-lives for investigational drugs

AMEND #2: 2016-JAN-04; AMEND #3: 2016-AUG-24

Not permitted:

- prior treatment with buparlisib (BKM120)

Radiation:

Patients may have had radiation, provided a minimum of 21 days has elapsed prior to enrollment. (Exceptions may be made for low dose palliative radiotherapy. Please call CCTG at [contact] PRIOR to registration if questions arise about the interpretation of this criterion). Patients must have recovered from any acute toxic effects from radiation prior to registration.

Surgery:

Previous surgery is permitted provided that wound healing has occurred and at least 14 days have elapsed if surgery was major.

5.1.7 Laboratory Requirements

(must be done within 7 days prior to registration)

Hematology	Absolute neutrophil counts (ANC)	$\geq 1.0 \times 10^9/L$
	Platelets	$\geq 50 \times 10^9/L$ and more than 5 days since last transfusion
Chemistry	Creatinine clearance*	$\geq 50 \text{ mL/min}$
	Bilirubin**	$\leq 1.5 \times \text{upper normal limit (UNL)}$
	Alanine aminotransferase (AST) and aspartate aminotransferase (ALT)	$\leq 1.5 \times \text{UNL}$ $\leq 3 \times \text{UNL}$ if hepatic involvement with CLL
	Potassium and calcium	Within normal limits for laboratory (supplementation permitted)
	Glucose (fasting)	$< 7.8 \text{ mmol/L}$ (AND HbA1c $\leq 8\%$ if diabetic)

* Creatinine clearance as calculated by Cockcroft-Gault formula or by 24 hour urine measurement:

Females:
$$\text{GFR} = \frac{1.04 \times (\text{140-age}) \times \text{weight in kg}}{\text{serum creatinine in } \mu\text{mol/L}}$$

Males:
$$\text{GFR} = \frac{1.23 \times (\text{140-age}) \times \text{weight in kg}}{\text{serum creatinine in } \mu\text{mol/L}}$$

** Direct if patient known to have Gilbert's syndrome

AMEND #1: 2015-OCT-22; AMEND #3: 2016-AUG-24

5.1.8 Patient consent must be obtained according to local Institutional and/or University Human Experimentation Committee requirements. It will be the responsibility of the local participating investigators to obtain the necessary local clearance, and to indicate in writing to the CCTG Study Coordinator that such clearance has been obtained, before the trial can commence in that centre. Because of differing requirements, a standard consent form for the trial will not be provided but a sample form is provided on the IND.216 webpage. A copy of the initial REB approval and approved consent form must be sent to the central office. The patient must sign the consent form prior to registration and prior to tests which are considered to be study specific (see Section 6). Please note that the consent form for this study must contain a statement which gives permission for the CCTG and monitoring agencies to review patient records.

5.1.9 Patients must be accessible for treatment and follow-up. Patients registered on this trial must be treated and followed at the participating centre. This implies there must be reasonable geographical limits (for example: 1 ½ hour's driving distance) placed on patients being considered for this trial. (Please call CCTG at [contact] if questions arise regarding the interpretation of this criterion.) Investigators must assure themselves that patients registered on this trial will be available for complete documentation of the treatment, adverse events, and follow-up.

5.1.10 In accordance with CCTG policy, protocol treatment is to begin within 2 working days of patient registration.

5.2 Ineligibility Criteria

Patients who fulfill any of the following criteria are not eligible for admission to the study:

5.2.1 Progression to high grade lymphoma (Richter's transformation) or myelodysplasia.

5.2.2 Patients with a history of other malignancies, except those which have been curatively treated and require no ongoing therapy.

5.2.3 Patients with known hypersensitivity to the study drug or its excipients.

5.2.4 The following are exclusions for enrolment on the study:

- Pregnant or lactating women. (N.B. All women of childbearing potential must have a negative serum or urine pregnancy test within 7 days prior to registration).
- Men and women of childbearing potential who do not agree to use adequate contraception (barrier method of birth control or abstinence, see Section 11.3.1)
 - prior to study entry
 - while taking buparlisib
 - and after completion of study therapy for 12 weeks in men and 4 weeks in women.

(Should a woman become pregnant or suspect she is pregnant, or should a man father a child, while participating in this study, she/he should inform the treating physician immediately).

5.2.5 Serious illness or medical condition which would not permit the patient to be managed according to the protocol, including, but not limited to:

- a) active uncontrolled or serious infection (viral, bacterial or fungal);
- b) pulmonary disease requiring oxygen;
- c) known HIV infection or other immune deficiency disorders (except for CLL);

AMEND #1: 2015-OCT-22; AMEND #2: 2016-JAN-04

- d) uncontrolled auto-immune hemolytic anemia (AIHA) or auto-immune thrombocytopenia (ITP)
- e) acute or chronic pancreatitis

5.2.6 Uncontrolled or significant cardiovascular disease including:

- Myocardial infarction within 12 months
- Uncontrolled angina within 6 months
- Clinically significant congestive heart failure (eligible if controlled and LVEF $\geq 50\%$)
- Stroke, TIA or other ischemic event within 12 months
- Severe cardiac valve dysfunction
- Left ventricular ejection fraction $< 50\%$ (only required if symptoms suggestive or history of cardiovascular disease)
- Uncontrolled hypertension

5.2.7 Patient has any of the following mood disorders:

- Medically documented history of or active major depressive episode, bipolar disorder (I or II), obsessive-compulsive disorder, schizophrenia, a history of suicidal attempt or ideation, or homicidal ideation (e.g. risk of doing harm to self or others)
- Score of ≥ 12 on the PHQ-9 questionnaire (posted on IND 216 website)
- Score of ≥ 15 on the GAD-7 mood scale (posted on IND 216 website)
- \geq CTCAE Version 4.0 grade 3 anxiety
- Patient selects a positive response of '1,2,3' to question 9 (suicidal ideation) in the PHQ-9 questionnaire

5.2.8 Patients who have received prior buparlisib (BKM120).

5.2.9 Patients with impairment of gastrointestinal (GI) function or GI disease that may significantly alter the absorption of buparlisib (e.g. ulcerative diseases, uncontrolled nausea, vomiting, diarrhea, malabsorption syndrome, or small bowel resection).

5.2.10 Patients who are unable to swallow capsules.

5.2.11 Patients on strong CYP3A inhibitors/inducers or therapeutic doses of warfarin-like anticoagulants (must have discontinued ≥ 7 days prior to day 1). Patients may receive low molecular weight heparin if indicated. See Appendix VII for a list of prohibited medications.

5.2.12 Patients on drugs with a known risk to induce Torsades de Pointes (see Appendix VIII).

5.2.13 Patients receiving high dose steroid therapy or another immunosuppressive agent. Note: Topical applications (e.g. rash), inhaled sprays (e.g. obstructive airways diseases), eye drops or local injections (e.g. intra-articular) are allowed. Patients who are on stable moderate dose corticosteroid treatment for treatment of conditions other than CLL (\leq dexamethasone 4 mg/day, prednisone 25 mg/day) for at least 14 days before start of study treatment are eligible.

5.2.14 Patients with known HIV positivity.

5.2.15 Patients with known CLL involvement of the central nervous system.

AMEND #1: 2015-OCT-22; AMEND #3: 2016-AUG-24

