11.3.1 Pregnancy Prevention

WOCBP and males who are enrolled in the trial must be informed of the requirement to use appropriate contraception. Investigators are advised to inform the female partners of male participants when appropriate and compliant with local policy.

AMEND #1: 2015-OCT-22; AMEND #3: 2016-AUG-24

Sexually active males should use a condom during intercourse while taking drug and for 12 weeks after the final dose of study treatment. A condom is required to be used also by vasectomized men in order to prevent delivery of the drug via seminal fluid.

WOCBP must use highly effective contraception while taking drug and for at least 4 weeks after the final dose of study treatment. Highly effective contraception is defined as

- i. total abstinence
- ii. male partner sterilization
- iii. use of a combination of both:
 - a. placement of an intrauterine device (IUD) or intrauterine system (IUS) AND
 - b. barrier methods of contraception: condom or occlusive cap (diaphragm or cervical /vault camps) with spermicidal foam/gel/film/cream/vaginal suppository

Note hormonal contraception methods (oral, injected and implanted) are not allowed as buparlisib decreases the effectiveness of hormonal contraceptives.

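### Section 5.2.4 reads as accepting a barrier method alone for women of childbearing potential; Section 11.3.1 accepts a barrier only together with an IUD or IUS

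*Protocol*

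**What the plan says.** Section 5.2.4 of the protocol is an exclusion criterion. It covers men and women of childbearing potential in one sentence and rules out those who do not agree to "adequate contraception (barrier method of birth control or abstinence, see Section 11.3.1". It then lists when contraception is to be used: before entry, during treatment, and for 12 weeks (men) or 4 weeks (women) afterwards.

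Section 11.3.1 separates the sexes. For women, "WOCBP must use highly effective contraception while taking drug and for at least 4 weeks after the final dose of study treatment". It gives three acceptable routes:

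- total abstinence;
- "male partner sterilization";
- a combination of two components, the first being "placement of an intrauterine device (IUD) or intrauterine system (IUS) AND" and the second "barrier methods of contraception: condom or occlusive cap", with spermicide.

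The same section disallows hormonal contraception because buparlisib makes it less effective. For men, "Sexually active males should use a condom during intercourse while taking drug and for 12 weeks after the final dose of study treatment".

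The SAP says nothing on contraception, and would not be expected to.

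**The concern.** The two sections give different answers to one practical question: is a barrier enough for a woman of childbearing potential? The parenthesis in 5.2.4 says yes on its face. Section 11.3.1 says no unless an IUD or IUS is also in place.

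The place of the looser wording matters. Section 7.1 has the site confirm the Section 5.0 requirements at registration, and Section 5.1 allows no exceptions to them. The eligibility lists in the treatment schema do not mention contraception, so 5.2.4 is the eligibility text on the subject. A site that screens from the words in the parenthesis could register a woman whose contraception falls below the protocol's own standard. One plausible route is a woman who must give up a hormonal method and reads 5.2.4 as saying that a barrier will do instead.

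What is at stake is participant safety and consistent screening across centres.

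**Working it through.** No arithmetic applies. The check is to set the two sections side by side for women of childbearing potential.

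| Method | Words of the 5.2.4 parenthesis | Section 11.3.1 |
|---|---|---|
| Total abstinence | accepted | accepted |
| Barrier as the only method | accepted | not accepted |
| IUD or IUS plus barrier with spermicide | accepted (a barrier is in use) | accepted |
| Sterilised male partner, no barrier | not named | accepted |

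**Step 1, the barrier.** In 5.2.4 a barrier and abstinence are alternatives, so either one satisfies the phrase. In 11.3.1 a barrier appears among the women's options only as the second half of a combination, joined to the IUD or IUS by a capitalised AND. A barrier alone therefore passes one section and fails the other.

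**Step 2, the sterilised partner.** This is a complete route in 11.3.1. The parenthesis in 5.2.4 omits it, so on the literal words a woman relying on it would be excluded. This difference runs in the stricter direction and raises no safety question. It does show that the parenthesis is not a faithful summary of 11.3.1.

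**Step 3, spermicide.** Section 11.3.1 mentions spermicide with the barrier component; 5.2.4 does not. The grammar leaves it open whether spermicide goes with the condom as well as the cap. The point does not depend on this, since a barrier alone fails 11.3.1 either way.

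**Step 4, durations.** The post-treatment periods agree: 12 weeks for men and 4 weeks for women in both sections. The conflict is about method only.

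**Step 5, how many patients.** Section 14.2 anticipates up to 29 patients overall (12 evaluable in the naïve cohort plus at most 17 in the exploratory cohort). The documents give no split by sex or childbearing potential, so no count can be derived.

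**The case against.** The strongest reply is that 5.2.4 is not free-standing. Its parenthesis ends by sending the reader to 11.3.1, which is the more specific text, separates the sexes and uses the word must. A site goes wrong only if it reads part of a parenthesis and ignores the rest. There are other safeguards. Section 11.3.1 requires these women to be told of the contraception requirement. Section 11.3 says the sample consent form carries general information on pregnancy prevention and the minimum period of use. Section 5.1.8 requires consent to be signed before registration.

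Most of this stands, and it is why the point is small. It does not dispose of the conflict. A pointer that follows a stated rule can be read as further detail on that rule, and here the stated rule differs from the one pointed to. The sample consent form is not among the documents, so whether it names the acceptable methods is unknown.

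A reader might infer more than the documents support, in three ways:

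- **That the sections also conflict for men.** They do not in any practical sense. A condom is a barrier, and it is the barrier a man would use. The occlusive cap in 11.3.1 is listed only among the options for women. The clause "A condom is required to be used also by vasectomized men in order to prevent delivery of the drug via seminal fluid" adds detail and contradicts nothing in 5.2.4.
- **That "prior to study entry" in 5.2.4 fixes when agreement must be given.** It is the first of three periods during which contraception is to be used, so it says nothing about when the method must be settled.
- **That the share of contraceptive combinations treated differently measures the size of the problem.** Combinations are not patients and their frequencies are unknown, so such a share would say nothing about risk.

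**Conclusion.** The inconsistency is real and limited to women of childbearing potential. The eligibility wording admits a barrier as the sole method, which 11.3.1 does not accept, and it leaves out the sterilised-partner route, which 11.3.1 does accept. Only the first difference bears on safety.

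The size is low. The number of patients affected is unknown and, as a matter of judgement, probably very small, given the planned total and the pointer to 11.3.1. The response rate, its decision rule, the sample size and the secondary analyses are unaffected.

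The conclusion rests on two readings: that the *or* in 5.2.4 makes a barrier sufficient by itself, and that 11.3.1 is the intended standard. Both are the plain sense of the text. It would go too far to infer that the protocol as a whole permits barrier-only contraception for these women, because 11.3.1 is mandatory and 5.2.4 refers to it.

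**What to change.** In Section 5.2.4, replace the parenthesis with *(as defined in Section 11.3.1 for men and for women of childbearing potential)*. Leave Section 11.3.1 unchanged.

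The method rule then stands in one place, both differences disappear, and the men's requirements carry over in full without being restated. The change is one phrase and can travel with any amendment. It has no effect on data collection, sample size or analysis.
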